# I. HYPOTHESES AND SPECIFIC AIMS/PURPOSE

# A. Statement of Purpose

The purpose of this study is to evaluate the safety, dose-requirements, and exploratory efficacy of twice-daily subcutaneous enoxaparin as in-hospital venous thromboembolism (VTE) prophylaxis in children (birth to 18 years) hospitalized with signs and/or symptoms of SARS-CoV-2 infection (i.e., COVID-19) including COVID-19 multisystem inflammatory syndrome (CMIS)

# B. **Principal Aims and Hypotheses**

**Specific Aim 1:** To investigate the safety of in-hospital thromboprophylaxis with twicedaily low-dose enoxaparin thromboprophylaxis (starting dose, 0.5 m/gkg subcutaneously q12 hours, adjusted to achieve a 4 hour post-dose anti-factor Xa level of 0.20-0.49 anti-Xa U/mL) in children hospitalized with COVID-19 related-illnesses, as measured by the cumulative incidence of ISTH-defined [10] clinically-relevant bleeding (primary endpoint).

Hypothesis 1: The observed cumulative incidence of ISTH-defined clinicallyrelevant bleeding is ≤2.6% (upper limit of 90% confidence interval: ≤11.8%) among children with COVID-19 who receive in-hospital thromboprophylaxis with twicedaily low-dose enoxaparin.

**Specific Aim 2:** To determine the median twice-daily enoxaparin dose, as measured in mg/kg, required to achieve a 4 hour post-dose anti-factor Xa level of 0.20-0.49 anti-Xa U/mL in children hospitalized with COVID-19 related-illnesses, and to compare dose-requirements by age group (birth to <1 year old, 1-<6 years old, 6-<13 years old, and 13-<18 years old).

Hypothesis 2: Median dose-requirement for anti-Xa-targeted thromboprophylaxis with twice-daily enoxaparin, as measured in mg/kg, in children hospitalized with COVID-19 are associated with age, with younger age groups requiring higher doses.

**Specific Aim 3 (Exploratory):** To investigate, on an exploratory basis, the efficacy of inhospital thromboprophylaxis with twice-daily enoxaparin in children hospitalized with COVID-19, as measured by the proportion of serial D-dimer levels obtained at standardized time points that are <2 times the upper limit of normal (<2x ULN) values for age (Aim 3a; surrogate marker of efficacy), the cumulative incidence of radiologicallyconfirmed HA-VTE (Aim 3b; clinical efficacy), and the median duration of in-hospital increased respiratory support (new requirement for high-flow nasal cannula, non-invasive ventilation, and/or mechanical ventilation, relative to any at-home baseline requirement; Aims 3c, clinical efficacy).

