# E. Description of Population to be Enrolled

#### 1. Target Enrollment

The target accrual is based on the primary endpoint (safety). The safety population is defined as all patients who received at least one dose of the enoxaparin regimen. In order to achieve adequate power and precision for determination of safety in the primary analysis (see also section G, below), the target enrollment is 38 evaluable children, from among a total of 12-15 participating sites. Participants who do not received at least one dose of the enoxaparin regimen (i.e. early termination, withdrawal of consent) will be replaced. Anticipating an 85% retention rate, we will enroll up to 45 participants. Both males and females of all races and ethnic groups are eligible for this study.

Table 1. Schedule of Assessments.

Assessment	Screening (Within 72 hours of hospital admission)	Enrollm ent Day 0	Day 1	Day 2	Day 3 *	Day 7 *	Day 14 *	Day 30 (+/- 2 days)
Informed consent		Х						
Enrollment		Х						
Full H&P	Х							
Focused H&P			Х	Х	Х	Х	Х	
Weight	Х							
CBC with platelet count	Х				Х	Х	Х	
PT and aPTT 	Х				Х	Х	Х	
Fibrinogen 	Х				Х	Х	Х	
Serum creatinine	Х				Х	Х	Х	
Urine pregnancy screen 	Х							
Research blood specimen 		Х	Х	Х	Х	Х	Х	
Anti-factor Xa level 			Х	+/- X				
SAE Monitoring			Х	Х	Х	Х	Х	Х
Bleeding event (based on focused interim H&P)			Х	Х	Х	Х	Х	Х
VTE event (based on focused interim H&P, with radiological confirmation when suspected clinically)			х	х	х	х	х	х
Telephone visit 								Х

Obtained for research purposes if not already being obtained clinically.

 For participants <20kg: (1) 3ml blue top tube and (1) 4mL CPT Tube (7mL total). For participants  $\ge$ 20kg, (1) 3mL blue top tube and (2) 4mL CPT tubes (11mL total). Research blood collection is for central research lab testing of D-dimer, Clot Formation and Lysis (CloFAL) assay, IL-6, and anti-SARS-CoV-2 IgG, as well as banking plasma, DNA isolated from the buffy coat, and peripheral blood mononuclear cells (PBMCs) for future research.

 Obtained at 4 hours after 1st or 2nd dose of enoxaparin, at initial dosage (mg/kg) and any subsequent change in dosage.

Focused, scripted assessment of symptoms of potential concern for bleeding events, VTE events, and SAEs. Refer to Manual of Operations.

\* If still hospitalized.

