# H. Data Analysis Plan:

The statistical analysis plan was developed by the lead trial biostatistician. Subject demographics and characteristics at study entry will be summarized with counts and percentages for categorical variables, and with means, standard deviations, medians, and interquartile ranges (IQR) as appropriate, for numeric variables. Missing data will not be imputed. Analysis of the primary endpoint will be conducted on the safety population, which includes all subjects who receive at least one dose of enoxaparin. The primary endpoint, cumulative incidence of ISTH-defined [11] clinically-relevant bleeding events during hospitalization, will be calculated with the corresponding exact (Clopper-Pearson) 90% confidence intervals (90%CIs). The precision of estimates for different cumulative incidences of clinically-relevant bleeds and corresponding 90% Cis are as follows: 0/38, 0% (0-7.6)%; 1/38, 2.6% (0-11.8%); 2/38, 5.3% (0-15.7%). The secondary endpoint, twice-daily enoxaparin dose required to achieve target anti-Xa levels, will be summarized

with medians and IQRs for all the study participants combined and by age group. Medians will be compared across age groups, if there are adequate numbers in the groups, using the Kruskal-Wallis test and a *post-hoc* Bonferroni-adjusted Mann-Whitney U test, if needed. The tertiary endpoints (as outlined in Section IV.B) will be calculated as proportions and cumulative incidences with 90%CIs, and medians with IQRs.

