2.5. SAMPLE SIZE

The study enrolled 38 participants

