4.5 STUDY POWER

With a sample size of 38 patients in the safety population, the precision of estimates for various cumulative incidences of clinically-relevant bleeding (with corresponding 90% CIs) was as follows: 0/38, 0% (0-7.6%); 1/38, 2.6% (0-11.8%); 2/38, 5.3% (0-15.7%).

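### Hypothesis 1's cut-offs copy the printed row for 1 bleed in 38, but the planned exact interval for 1/38 misses them, and they leave no slack for fewer than 38 analysed children

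*Protocol*

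**What the plan says.** Hypothesis 1 (Protocol I.B) reads: "The observed cumulative incidence of ISTH-defined clinicallyrelevant bleeding is ≤2.6% (upper limit of 90% confidence interval: ≤11.8"%). Protocol IV.H and SAP 4.2 give the method; in the protocol's words, the incidence "will be calculated with the corresponding exact (Clopper-Pearson) 90% confidence intervals (90%CIs"). The precision figures in Protocol IV.H are "1/38, 2.6% (0-11.8%); 2/38, 5.3% (0-15.7"%), and SAP 4.5 repeats them, introduced by "With a sample size of 38 patients in the safety population".

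On the denominator, Protocol IV.E.1 says "the target enrollment is 38 evaluable children" and "Anticipating an 85% retention rate, we will enroll up to 45 participants". Undosed children are replaced. The protocol's primary analysis set is simple: "The safety population is defined as all patients who received at least one dose of the enoxaparin regimen".

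SAP 2.5 states "The study enrolled 38 participants". SAP 4.1.1 then keeps only children who had no eligibility violation, were dosed, and had the primary outcome determined within 30 days of COVID diagnosis. SAP 4.1.4 adds complete-case analysis without imputation.

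SAP 4.2 has no criterion of its own. Neither document states a bleed count for the final analysis, a cut-off for any denominator other than 38, or an assumed true bleeding rate.

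**The concern.** The two cut-offs are percentages taken from one specific result, 1/38, and they raise two problems.

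First, the printed upper limit is not the one the planned method gives. The result the hypothesis was built around can therefore be called a pass from the printed table and a miss from the computed interval.

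Second, 1/38 sits at the edge of both cut-offs. Any smaller denominator turns the benchmark into a zero-bleed requirement without saying so. The SAP's analysis set makes a smaller denominator possible. A child can be dropped on timing alone: the protocol's final contact is 30 days (±2) after enrolment, the SAP counts 30 days from diagnosis, and the qualifying test may be up to 7 days before enrolment.

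At stake is whether the stated safety hypothesis is reported as met when one child bleeds. That could depend on which printed figure is used, or on whether a child who did not bleed is counted.

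**Working it through.** **Inputs.** Cut-offs ≤2.6% and ≤11.8% (Protocol I.B). Exact two-sided 90% interval (Protocol IV.H, SAP 4.2). N=38 (Protocol IV.E.1, SAP 2.5 and 4.5). Enrolment ceiling 45 (Protocol IV.E.1), which reproduces: 38/0.85 = 44.7. The true bleeding rate p is not given, so 1%, 2.6% and 5.6% are assumptions. The 5.6% is the rate cited in Protocol IV.K.1 for children on thromboprophylaxis; it covers major plus minor bleeding, so it is not the same endpoint.

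**Reproducing the printed table.** With x bleeds in n children, the upper limit is the 0.95 quantile of Beta(x+1, n−x) and the lower limit is the 0.05 quantile of Beta(x, n−x+1), or 0 when x=0.

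| Result | Printed | Computed |
|---|---|---|
| 0/38 | 0–7.6% | 0–7.58% |
| 1/38 | 0–11.8% | 0.13–11.885% |
| 2/38 | 0–15.7% | 0.94–15.66% |

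The upper limits for 0/38 and 2/38 reproduce. The one for 1/38 does not: it rounds to 11.9%. As a direct check, at p = 11.8% the chance of 0 or 1 bleed in 38 is 5.15%, still above 5%, so the limit must lie above 11.8%. Agresti-Coull gives 11.80% for 1/38 but 7.94% and 15.32% for the other rows. Of the interval methods tried (exact, one-sided, Wilson, Agresti-Coull, Jeffreys, Wald), none gives all three printed upper limits.

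**One bleed at other denominators.**

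| Result | Observed | Upper 90% limit | Both cut-offs met? |
|---|---|---|---|
| 1/36 | 2.78% | 12.51% | no, fails both |
| 1/37 | 2.70% | 12.19% | no, fails both |
| 1/38 | 2.63% | 11.885% | only on the printed figures |
| 1/39 | 2.56% | 11.60% | yes |
| 1/45 | 2.22% | 10.11% | yes |

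Zero bleeds passes and two bleeds fails at every N from 34 to 45 (2/45 is 4.44%, upper limit 13.34%). The reading therefore matters only when exactly one child bleeds.

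**Chance of meeting Hypothesis 1.** If 1/38 counts as a pass, at N=38 it is (1−p)^38 + 38p(1−p)^37. If it does not, it is (1−p)^38. At N=37 it is (1−p)^37. For p = 0.026 the first is 0.3675 + 0.3728 = 0.7403 and the last is 0.3773.

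| Assumed true rate | N=38, 1/38 accepted | N=38, strict | N=37 |
|---|---|---|---|
| 1% | 94.5% | 68.3% | 68.9% |
| 2.6% | 74.0% | 36.8% | 37.7% |
| 5.6% | 36.4% | 11.2% | 11.9% |

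The difference between the first two columns is the chance of exactly one bleed in 38: 26%, 37% and 25% respectively.

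**The case against.** The strongest reply is that Hypothesis 1 is an expectation written under the aims, not a decision rule. The analysis sections plan estimation only, and no passage ties a go/no-go decision or a declaration of safety to it. The bleeding rule with operational effect is the enrolment pause in Table 2 (Protocol IV.J.2), which is already written in patient counts. A reader shown 1/37 (2.7%, upper limit 12.2%) instead of 1/38 (2.6%, upper limit 11.9%) has almost the same evidence. This stands, and it limits the weight of the point. It does not remove it: a stated hypothesis will be reported as met or not met.

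A second reply is that the protocol protects the denominator. It analyses every dosed child, replaces undosed children and allows 45 enrolments to reach 38. This also stands. Under that population the planned N is 38 or more, and the risk of falling below 38 comes from the SAP's narrower set. Equally, denominators of 39 to 45 are possible under the protocol's ceiling but not if enrolment ended at 38.

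A reader might infer that losing one child cuts the chance of success from 74% to 38%. The documents do not support that as a general statement. It needs a true rate of 2.6%, which they never state as a design assumption, and it needs the misprinted 11.8% to be accepted. On the planned method one bleed in 38 already misses the cut-off, and nothing drops. It also needs the child who leaves not to be the one who bled. A reader might also take 85% of 38 as a likely analysed number, but the 38 already allows for the 15% loss.

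**Conclusion.** The point holds as a correction to a wrong threshold and an unstated denominator. Hypothesis 1's upper limit is 0.085 percentage points below the planned exact limit for the result it was taken from (11.885 − 11.8), and that gap is enough to reverse the reading of one bleed in 38. Below N=38, one bleed fails both parts; at N=39 or more it passes both.

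The practical effect is confined to the case of exactly one bleed, about a 37% chance at N=38 if the true rate is 2.6% and about 25% at 1% or 5.6%. The arithmetic for the intervals rests only on the documents' method and counts. The probabilities rest on assumed true rates. That fewer than 38 children might be analysed follows from SAP 4.1.1 and 4.1.4; how likely it is cannot be derived from the documents. Because the plan is one of estimation, this is a clarification that should be made, not a flaw that undermines the trial.

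**What to change.** Before the analysis:

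1. Restate Hypothesis 1 and add the same sentence to SAP 4.2: at most one child with an adjudicated clinically-relevant bleed among all children dosed at least once (target N=38), with the exact 90% interval reported at the actual N.
2. Correct the upper limit to 11.9% in Protocol I.B, and the 1/38 interval to 0.1% to 11.9% in Protocol IV.H and SAP 4.5. The lower limit for 2/38 in the same table should read 0.9%.
3. In SAP 4.1.1, use the protocol's all-dosed population for the primary endpoint.
4. Give enrolled, dosed and analysed counts separately in SAP 2.5, and recompute SAP 4.5 at the analysed N.

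The cost is wording in both documents. The stated upper limit becomes slightly less favourable: 11.9% at N=38, and 12.2% if N turns out to be 37. A count rule also settles the ambiguity in the lenient direction. At N=37 and an assumed true rate of 5.6%, the chance of meeting the hypothesis is 38% under the count rule, against 12% under the percentage cut-offs. Since the trial is open-label and SAP 2.5 reports enrolment in the past tense, the change should be dated and should say whether bleed counts were already known.

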# II. BACKGROUND AND SIGNIFICANCE

VTE is a serious condition in children associated with significant morbidity. Adverse VTE outcomes include VTE-related mortality, recurrent VTE, and development of chronic venous insufficiency following deep venous thrombosis (post-thrombotic syndrome). Given these adverse outcomes, as well as recent recognition of VTE as the second leading cause of preventable harm in hospitalized children (after central line associated blood stream infections; CLABSI) [1], a national patient safety initiative in the U.S., supported by the Children's Hospitals Association Solutions for Patient Safety network, has been undertaken to reduce the incidence of hospital-associated VTE (HA-VTE) in children. While pharmacological thromboprophylaxis with various anticoagulants (including low molecular weight heparins and the direct oral anticoagulants) has been shown to be safe and effective in hospitalized adults, both safety and efficacy among hospitalized children have yet to be fully established.

In order to optimize benefit-risk ratio for target populations in future trials of anticoagulant thromboprophylaxis in hospitalized children, the PI and colleagues have developed risk models for HA-VTE in several important hospitalized pediatric populations, including noncritically ill children, critically-ill children without underlying cardiac disease, and criticallyill children following cardiac surgery or cardiac catheter-based therapeutic intervention [2–5]. These models share common features of central venous catheterization, severe infection or systemic inflammatory state, and anticipated length of stay (LOS) >3 days as statistically-significant, independent risk factors for HA-VTE in hospitalized children. In the absence of efficacy and safety data from pediatric trials, clinicians across the U.S., Canada, Europe and many other countries/regions have, in recent years, used low-dose low molecular weight heparins (LMWH; most often, enoxaparin) as primary thromboprophylaxis in hospitalized children who exhibit these and/or other high-risk features for the development of in-hospital VTE.

A novel coronavirus, SARS-CoV-2, is responsible for a rapidly spreading pandemic that has reached 160 countries, causing infection in over 500,000 individuals, and 25,000 deaths, as of April 1, 2020. The SARS-CoV-2 illness, known as COVID-19, exhibits a range of disease severity, from asymptomatic infection to respiratory failure, multi-organ failure, and death. Among hospitalized patients, COVID-19 is characterized by atypical pulmonary infiltrates and a severe inflammatory response with which marked coagulation activation, as evidenced by marked elevation in plasma D-dimer levels. A recent retrospective analysis from China demonstrated reduced mortality and reduced LOS among hospitalized patients (primarily adults) with COVID-19 and markedly-elevated Ddimers who received anticoagulation (predominantly, LMWH) [6]. Accordingly, the International Society on Thrombosis and Haemostasis (ISTH) has recently recommended prophylactic anticoagulation be strongly considered in patients hospitalized for COVID-19 [7]. Similarly, the American Society of Hematology has recommended that "all patients hospitalized with COVID-19 should receive pharmacologic thromboprophylaxis" and recommend participation in "well-designed clinical trials and/or epidemiologic studies when they become available." [8] Children with COVID-19 have also presented with

CMIS, a Kawasaki-disease-like illness, presenting with severe systemic inflammatory disease affecting multiple systems beyond the respiratory system. [9]

Hospitalization of children infected with SARS-CoV-2 have increased across many children's hospitals in the U.S. with nearly 1% of the infected pediatric population anticipated to develop acute respiratory distress syndrome [10]. Many children hospitalized with COVID-19 are exhibiting markedly elevated D-dimer levels [11] much as has been observed in hospitalized adults, and it is expected that these children will similarly exhibit a heightened VTE risk. Based on this urgent and time-sensitive clinical need, and given that anticoagulant prophylaxis against HA-VTE in children is used selectively in routine care at children's hospitals across the U.S. but is not yet supported by safety data from multicenter clinical trials, the objective of this proposal is to rapidly conduct a phase 2 multicenter trial of low-dose enoxaparin thromboprophylaxis in children newly-hospitalized with COVID-19. The study proposed herein will leverage an existing network and clinical coordinating center (CCC) infrastructure of the NIH NHLBI U01 Prospective Multi-Center Evaluation of the Duration of Therapy for Thrombosis in Children (Kids-DOTT).

This proposal is significant in that it addresses a critical need for establishing safety of prophylactic anticoagulation in hospitalized children who are at heightened risk for HA-VTE. Furthermore, this proposal is innovative, in that it seeks to establish first multicenter evidence on safety of prophylactic anticoagulation for the prevention of HA-VTE in children, with a focus on the especially-heightened VTE risk population of pediatric patients hospitalized with COVID-19 related-illnesses. The work under this supplement is a logical extension of the parent award, and will provide complementary knowledge to the findings derived from the Kids-DOTT trial, addressing a critical gap in knowledge in the pediatric VTE field. The proposed trial addresses the same problem as the parent award (i.e., VTE in children) and employs the same therapeutic agents (i.e., conventional anticoagulants, which have consisted of the LMWH enoxaparin in >95% of patients).

# III. PRELIMINARY STUDIES/PROGRESS REPORT:

Based on a PubMed search on 13April2020, no prior studies of safety, dose-requirement, and/or efficacy of twice-daily enoxaparin thromboprophylaxis in hospitalized children, with or without COVID-19, have been published. Based on clinicaltrials.gov and eudract.ema.europa.eu search on 13April2020, no such studies have been registered on clinicaltrials.gov or with EudraCT in Europe.

# IV. RESEARCH METHODS: SUMMARY OF STUDY RATIONALE

# A. Primary Outcome

PRIMARY SAFETY: Occurrence of clinically-relevant (i.e., major plus clinically relevant non-major [CRNM]) bleeding within 30 days.

Based upon International Society on Thrombosis and Haemostasis (ISTH) Scientific and Standardization Committee standardized definitions for pediatric trials [12], "Major bleeding" will be characterized by bleeding satisfying any one of the following criteria: 1) fatal; 2) clinically overt and associated with a decrease in hemoglobin of at least 2 g/dL in a 24 hour period; 3) clinically overt and for which blood product is administered; 4) retroperitoneal, pulmonary, or involving the central nervous system; 5) requiring surgical intervention in an operating suite.

"CRNM bleeding" definition includes any bleeding that does not fulfill the above criteria but fulfills one of the following: 1) Bleeding requiring medical or surgical intervention to restore hemostasis; 2) Bleeding for which medical attention is sought.

# B. Secondary Outcome(s)

DOSE REQUIREMENT: Median twice-daily enoxaparin dose, as measured in mg/kg, required to achieve a 4 hour post-dose anti-factor Xa level of 0.20-0.49 anti-Xa U/mL.

EXPLORATORY EFFICACY: Proportion of plasma D-dimer levels <2x ULN; cumulative incidence of VTE; and duration of assisted ventilation.

# C. Endpoint Adjudication

The primary safety outcome (clinically-relevant bleeding) and exploratory clinical efficacy outcome of recurrent VTE, as well as all death events, will be centrally adjudicated via an independent Clinical Endpoint Adjudication Committee (CEAC), using a standardized process delineated in the CEAC charter. Upon reporting of these outcome events, deidentified information on pertinent history, physical exam findings, imaging studies, laboratory studies, and other pertinent information from the medical record corresponding to these outcome events (clinically-relevant bleeds) will be submitted by the study team at participating sites for review by the clinical experts on the committee.

# D. Summary of Research Methods and Study Design

The study design is a phase 2, single-arm, open-label, non-randomized clinical trial conducted among the Kids-DOTT Investigators Group, at 12-15 of the Kids-DOTT participating centers. The list of participating Kids-DOTT centers (including primary and alternate/supplemental sites) is shown in Appendix 1. Study activity at each site will be

overseen by either a pediatric hematologist, pediatric intensivist, or pediatric hospitalist as the site principal investigator, in close collaboration with sub-investigators from the other two aforementioned specialties.

The Clinical Coordinating Center (CCC) and Data Coordinating Center (DCC) for this nonblinded, non-randomized phase 2 trial are at Johns Hopkins All Children's Hospital (JHACH; St. Petersburg, FL), led by Johns Hopkins University School of Medicine faculty based on that campus (Appendix 2. CCC). Coordinating center personnel have extensive experience in the conduct of numerous large collaborative clinical trials, with specific expertise in pediatric phase 1-3 trials. CCC and DCC key personnel include:

Overall (National) Principal Investigator: Steering Committee Chair: Clinical Endpoint Adjudication Ctte Chair: Data and Safety Monitoring Board Chair: Medical Safety Officer: Multi-Site Project Managers:

Lead Biostatistician: Biorepository Manager: [name], MSc [name], PhD [name] [name], MPH [name], PhD [name], MS (CCC) [name], MBA-IT (DCC) [name] [name], MS, MT

Anticoagulant (low-dose enoxaparin) thromboprophylaxis dosing regimen is as follows for inpatient use only:

- Enoxaparin starting dose 0.5 mg/kg (max starting dose: 60 mg) subcutaneously q12 hours, adjusted to achieve a 4 hour post-dose anti-factor Xa level of 0.20-0.49 anti-Xa U/mL after the 1st or 2nd dose.
  - For anti-Xa values <0.20 U/mL, the enoxaparin dose will be increased by 10-20%, and a 4 hour post-dose anti-Xa level will be obtained after the 1st or 2nd dose at the new dosing regimen.
  - For anti-Xa values ≥0.5 U/mL, the enoxaparin dose will be decreased by 10-20%, and a 4 hour post-dose anti-Xa level will be obtained after the 1st or 2nd dose at the new dosing regimen.

The Schedule of Assessments is shown in Table 1. SAE monitoring and safety laboratory monitoring occurs on days 1-3, and on days 7 and 14 if the patient is still hospitalized. For all participants, pertinent clinical data will be captured as follows: results of coagulation and thrombophilia testing; nature of any major or clinically-relevant non-major bleeding episodes (as defined in Section IV B, above) during the anticoagulant therapy period (with detail as to amount of any related blood transfusion and/or any other intervention required—see also Data and Safety Monitoring Plan section); and nature of any new onset VTE (with detail as to signs/symptoms and anatomic site). PDFs of the REDCap electronic case report forms (eCRFs), as well as SAE report forms, are provided in the Manual of Operations. All SAEs and enoxaparin regimen adherence will be tracked

throughout hospitalization, and SAEs will continue to be tracked through 30 days postenrollment.

Children will complete their participation in the trial at the 30 days (+/- 2 days) postenrollment end-of-study telephone visit. As noted previously, the primary safety endpoint collection also occurs at the 30 days (+/- 2 days).

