#### 30 days (+/- 2 days) after enrollment

Patient will be assessed for SAEs, bleeding events, and VTE events via telephone call with a study team member using a standardized screening script.

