# **Table 2.**Optimized Boundaries for Halting Enrollment (i.e., "Pause")Pending Further Evaluation by the DSMB.

#### 3. SAE Reporting Plan

SAEs will be collected from time of enrollment to the end of the 30 day study window. Diseases or conditions that were present prior to the time of randomization should not be counted as adverse events unless they increase in grade or severity during the timeframe described above.

*Adverse event:* Any untoward medical occurrence associated with the use of a drug in humans, whether or not considered drug related.

*Serious adverse event:* An adverse event is considered "serious" if, in the view of either the investigator or sponsor, it results in any of the following outcomes:

- Death
- A life-threatening adverse event
- Inpatient hospitalization or prolongation of existing hospitalization
- A persistent or significant incapacity or substantial disruption of the ability to conduct normal life functions
- A congenital anomaly/birth defect
- Important medical events that may not result in death, be life-threatening, or require hospitalization may be considered serious when, based upon appropriate medical judgment, they may jeopardize the patient or participant and may require medical or surgical intervention to prevent one of the outcomes listed in this definition. Examples of such medical events include allergic bronchospasm requiring intensive treatment in an emergency room or at home, blood dyscrasias or convulsions that do not result in inpatient hospitalization, or the development of drug dependency or drug abuse.

All SAEs will be reported within 24 hours of knowledge of the event. Please refer to the Manual of Operations for SAE reporting forms and guidelines.

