#### Bleeding Events:

- Major bleeds and clinically-relevant non-major (CRNM) bleeds will be considered SAEs of particular interest (if they occur during the AE reporting window).
- Based upon ISTH standardized definitions for pediatric trials [10], "Major bleeding" will be characterized by bleeding satisfying any one of the following criteria: 1) fatal;
  2) clinically overt and associated with a decrease in hemoglobin of at least 2 g/dL in a 24 hour period; 3) clinically overt and for which blood product is administered;
  4) retroperitoneal, pulmonary, or involving the central nervous system; 5) requiring surgical intervention in an operating suite.
- "CRNM bleeding" definition includes any bleeding that does not fulfill the above criteria but fulfills one of the following: 1) Bleeding requiring medical or surgical intervention to restore hemostasis, but not in an operating suite; 2) Bleeding for which medical attention is sought.

VTE events will be considered outcome events rather than SAEs, unless they otherwise fulfill the regulatory definition of an SAE (i.e., they will not fulfill the SAE criterion of investigator-defined "important medical events").

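### The call that collects the 30-day bleeding endpoint and ends participation may fall on Day 28 or 29, leaving a discharged child's last one or two days without scheduled ascertainment

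*Protocol*

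**What the plan says.** **Endpoint.** Protocol IV.A defines the primary outcome as "Occurrence of clinically-relevant (i.e., major plus clinically relevant non-major [CRNM]) bleeding within 30 days". SAP 3.1 gives the same 30-day horizon.

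**Collection.** Protocol IV.D reads "Children will complete their participation in the trial at the 30 days (+/- 2 days") and, in the next sentence, "As noted previously, the primary safety endpoint collection also occurs at the 30 days (+/- 2 days"). Table 1 and the visit list in IV.F repeat the window. The visit is a scripted call: "Patient will be assessed for SAEs, bleeding events, and VTE events via telephone call with a study team member using a standardized screening script". No contact is scheduled after it.

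**SAE tracking.** IV.D also says "SAEs will continue to be tracked through 30 days postenrollment", and IV.J.3 says "SAEs will be collected from time of enrollment to the end of the 30 day study window". Endpoint bleeds fall under this: "Major bleeds and clinically-relevant non-major (CRNM) bleeds will be considered SAEs of particular interest". In Table 1, however, the SAE row and the bleeding row both end at the Day 30 (+/- 2 days) column.

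**Analysis.** Protocol IV.H and SAP 4.2 both calculate the primary endpoint from bleeds during the hospital stay. SAP 4.1.1 admits a child to the analysis only if the outcome was determined within 30 days of the COVID diagnosis. SAP 2.5 states that 38 participants were enrolled.

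**The concern.** A proportion with a fixed 30-day horizon needs each child's status known through Day 30. A symmetric window lets the only scheduled post-discharge contact come before the horizon closes, and a call on Day 28 cannot ask about Days 29 and 30. Such a child would be counted bleed-free for the whole period unless a report reached the study by another route. Taken alone, the early side of the window can only lose events.

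The analysis is sensitive to single events. One bleed in 38 is the result on which Hypothesis 1 is built, and two in 38 would fail it.

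**Working it through.** **Inputs**

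- Evaluable children: 38 (Protocol IV.E.1).
- Horizon: 30 days (Protocol IV.A, SAP 3.1), counted here from enrollment as Day 0. IV.A does not state the anchor.
- Call window: Day 28 to Day 32 (Protocol IV.D, Table 1).
- Bleeding rates: 2.6% (Hypothesis 1) and 5.6% (the combined minor and major rate in Protocol IV.K.1, used as a stand-in because its definition is not that of the endpoint).
- Assumptions: bleeds spread evenly over the 30 days; all 38 children already discharged; nothing reported after an early call. The documents give no distribution of call dates, so two cases are shown.

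**Step 1. The plan's own intervals.** The two-sided 90% Clopper-Pearson upper limit is the 0.95 quantile of Beta(x + 1, 38 − x).

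| Bleeds | Upper limit, recomputed | Upper limit, stated |
|---|---|---|
| 0/38 | 7.58% | 7.6% |
| 1/38 | 11.89% | 11.8% |
| 2/38 | 15.66% | 15.7% |

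The upper limits reproduce, with 11.89% apparently truncated. None depends on the call window.

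**Step 2. Days lost per child.** A Day 28 call loses 2/30 = 6.7% of the period, and a Day 29 call 1/30 = 3.3%. With calls even over five days, 2/5 = 40% of children are called before Day 30, and the mean loss is (2 + 1 + 0 + 0 + 0)/5 = 0.6 day, or 0.6/30 = 2%.

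**Step 3. Expected missed bleeds** = 38 × rate × fraction of the period lost.

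| Call dates | Rate 2.6% | Rate 5.6% |
|---|---|---|
| Even over Days 28–32 (2%) | 38 × 0.026 × 0.02 = 0.02 | 38 × 0.056 × 0.02 = 0.04 |
| All on Day 28 (2/30) | 38 × 0.026 × 2/30 = 0.07 | 38 × 0.056 × 2/30 = 0.14 |

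In the Day 28 case the chance of missing at least one bleed is 1 − (1 − rate × 2/30)^38, which is 6% at 2.6% and 13% at 5.6%.

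**Step 4. Consequence of one missed bleed.** A true 2/38 would be reported as 1/38, and the upper limit would read 11.9% instead of 15.7%. This is what a miss would do. Step 3 shows how unlikely a miss is.

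**Step 5. The anchor in SAP 4.1.1.** The qualifying test may precede enrollment by up to 7 days (inclusion criterion 2). A call exactly on Day 30 can therefore fall 30 + 7 = 37 days after that test. If the criterion refers to when the determination is made, on-time calls would remove children from the analysis. A later call window without re-anchoring would remove more.

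**The case against.** The strongest reply is that the protocol already collects these bleeds. SAEs run through Day 30 and endpoint bleeds are SAEs, so a reader who infers that the last days go wholly unobserved goes further than the text allows. That stands. What remains is narrower: after an early call to a discharged child, the documents state a period but schedule nothing to cover its end. The call script is in the Manual of Operations, which is not available here and may address this.

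Other stronger readings also fail:

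- **Children still in hospital at Day 28 are the most exposed.** They are the best observed, because IV.D tracks all SAEs throughout hospitalization.
- **Late calls bring Day 31 or 32 bleeds into the count.** The 30-day definition already excludes them, and event dates are captured (Protocol IV.I). An explicit onset rule would only make this plain.
- **The estimate is materially biased downward.** The direction is right for early calls, but the expected loss is a small fraction of one event. Protocol IV.K.3 expects no increased bleeding risk beyond 12 hours after the inpatient regimen ends, so an even hazard probably overstates the loss after discharge.

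Finally, if the hospital-stay wording in IV.H and SAP 4.2 governs, an early call to a discharged child loses nothing. That is correct, but the wording contradicts the outcome defined in IV.A and SAP 3.1, so the sponsor can rely on it only by giving up the 30-day endpoint.

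**Conclusion.** The point holds as a minor, inexpensive improvement. A compliant Day 28 or 29 call leaves a discharged child with one or two days of a 30-day endpoint that no scheduled contact covers, and the stated SAE period has no visible mechanism after that call.

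The likely numerical effect is about 0.02 to 0.04 missed bleeds, and 0.07 to 0.14 in the extreme case. These figures rest on an even hazard, all 38 children discharged and no spontaneous reports, so they lean high. Sample size and the planned intervals do not change.

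The related inconsistency deserves at least as much attention. The endpoint period is 30 days in the outcome definitions and the hospital stay in the analysis text, while the population criterion counts 30 days from diagnosis. These must be reconciled for the 30-day call to have a defined role in the primary analysis.

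**What to change.** 1. **Window.** In Protocol IV.D, Table 1 and the IV.F visit list, allow the final contact only on or after Day 30 post-enrollment, for example Day 30 to Day 34, which keeps the five-day width.
2. **Counting rule.** In Protocol IV.H and SAP 4.2, replace the restriction to the hospital stay with bleeds whose onset falls from enrollment through Day 30.
3. **Population.** In SAP 4.1.1, anchor outcome determination to enrollment, worded so that a call within the permitted window does not exclude a child.
4. **Calls already made on Day 28 or 29.** Check the medical record through Day 30 where available, and report how many children were affected.

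With 38 children already enrolled, items 2 to 4 carry most of the value. The cost is wording changes, some calls up to two days later than now, and a small amount of record review. No patients or procedures are added.
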